6. Will you be recording any PHI when conducting the records review to identify potential subjects and/or determine eligibility?
 Yes. Describe:
 No
7. If you answered “Yes” to question 6 above, please describe when you will destroy identifiers (must be the earliest opportunity consistent with the conduct of the research) or provide justification for why they must be retained:
8. The PHI accessed or recorded for identification/screening purposes will not be reused or disclosed to (shared with) any other person or entity, except as required by law, for authorized oversight of the research study, or for other research for which the use or disclosure of the PHI would be permitted under the Privacy Rule.
 True

PROTOCOL TITLE: “*Evaluating the efficacy of micro-fragmented adipose tissue and intra-articular corticosteroid injections for symptomatic knee osteoarthritis: a randomized, placebo controlled study*”

False

B. Waiver of Documentation of Consent

Complete this checklist if you intend to obtain consent verbally but will not be obtaining signatures from subjects on a consent form to document consent. Waivers of documentation of consent are commonly requested when using scripts, information sheets, or email or survey introductions to present the elements of consent instead of using a traditional consent form.

1. Are you requesting a waiver of documentation of consent for some or all subjects?

All

Some. Explain:

2. Provide justification for one of the following:

a) That the only record linking the subject and the research would be the consent document and the principal risk would be potential harm resulting from a breach of confidentiality. Each subject will be asked whether the subject wants documentation linking the subject with the research, and the subject's wishes will govern.

b) That the research presents no more than minimal risk of harm to subjects and involves no procedures for which written consent is normally required outside of the research context.

3. Do you intend to provide subjects with a written statement regarding the research in lieu of a traditional consent form?

Yes. Please attach a copy to your submission in Click.

No

C. Alteration of Consent

Complete this checklist if you intend to obtain consent but will be eliminating or altering one or more of the required elements of consent. Alterations of consent are commonly requested for research involving deception or for minimal risk research when an abbreviated consent is desired and one or more of the required element are not relevant to the research.

PROTOCOL TITLE: “*Evaluating the efficacy of micro-fragmented adipose tissue and intra-articular corticosteroid injections for symptomatic knee osteoarthritis: a randomized, placebo controlled study*”

Note: FDA-regulated research is not eligible for an alteration of consent.

1. Which element(s) of consent do you wish to eliminate and why?

2. Which element(s) of consent do you wish to alter and why?

3. Provide justification for each of the following regulatory criteria:
 - a) The research involves no more than minimal risk to the subjects:

 - b) The waiver or alteration will not adversely affect the rights and welfare of the subjects:

 - c) The research could not practicably be carried out without the waiver or alteration:

 - d) Whenever appropriate, the subjects will be provided with additional pertinent information after participation:

D. Full Waiver of Consent/Parental Permission

Complete this checklist if you are requesting a full waiver of consent for all subjects or certain subject groups (e.g., retrospective cohort). Full waivers of consent are commonly requested when the research does not include any opportunity for interaction with subjects (e.g., chart review).

Note: FDA-regulated research is not eligible for a full waiver of consent using these criteria. If you believe that your FDA-regulated research may be eligible for a waiver under another mechanism, such as planned emergency research, contact the HRPO for assistance in determining what information to provide to the HRRC.

1. Are you requesting a waiver for some or all subjects?
 All
 Some. Explain:

2. Provide justification for each of the following regulatory criteria:
 - a) The research involves no more than minimal risk to the subjects:

PROTOCOL TITLE: “*Evaluating the efficacy of micro-fragmented adipose tissue and intra-articular corticosteroid injections for symptomatic knee osteoarthritis: a randomized, placebo controlled study*”

- b) The waiver or alteration will not adversely affect the rights and welfare of the subjects:
- c) The research could not practicably be carried out without the waiver or alteration:
- d) Whenever appropriate, the subjects will be provided with additional pertinent information after participation:

E. Full Waiver of Consent/Parental Permission (Public Benefit or Service Programs)

Complete this checklist if you are requesting a full waiver of consent for all subjects or certain subject groups (e.g., retrospective cohort) and the research involves the evaluation of a public benefit or service program.

1. Are you requesting a waiver for some or all subjects?
 - All
 - Some. Explain:
2. Provide justification for each of the following regulatory criteria:
 - a) The research or demonstration project is to be conducted by or subject to the approval of state or local government officials and is designed to study, evaluate, or otherwise examine: (i) public benefit or service programs; (ii) procedures for obtaining benefits or services under those programs; (iii) possible changes in or alternatives to those programs or procedures; or (iv) possible changes in methods or levels of payment for benefits or services under those programs:
 - b) The research could not practicably be carried out without the waiver or alteration.

F. Full Waiver of HIPAA Authorization

Complete this checklist if you are requesting a full waiver of the requirement to obtain HIPAA authorization for all subjects or certain subject groups (e.g.,

PROTOCOL TITLE: *“Evaluating the efficacy of micro-fragmented adipose tissue and intra-articular corticosteroid injections for symptomatic knee osteoarthritis: a randomized, placebo controlled study”*

retrospective cohort). Full waivers of HIPAA authorization are commonly requested when the research does not include any opportunity for interaction with subjects (e.g., chart review).

1. Are you requesting a waiver of authorization for some or all subjects?
 All
 Some. Explain:
2. Describe your plan to protect health information identifiers from improper use and disclosure:
3. Describe your plan to destroy identifiers at the earliest opportunity consistent with conduct of the research (absent a health or research justification for retaining them or a legal requirement to do so):
4. Describe why the research could not practicably be conducted without the waiver or alteration:
5. The PHI accessed or recorded for identification/screening purposes will not be reused or disclosed to (shared with) any other person or entity, except as required by law, for authorized oversight of the research study, or for other research for which the use or disclosure of the PHI would be permitted under the Privacy Rule.
 True
 False

G. Other Waiver Types

If you are seeking another waiver type (e.g., *Planned Emergency Research*, *Waiver of Parental Permission to Protect Child Participants*, *Enforcement Discretion for In Vitro Diagnostics*, etc. contact the HRPO office for assistance in determining what information to submit for the HRRC's consideration.

II. Vulnerable Populations

A. Adults with Cognitive Impairments

PROTOCOL TITLE: “*Evaluating the efficacy of micro-fragmented adipose tissue and intra-articular corticosteroid injections for symptomatic knee osteoarthritis: a randomized, placebo controlled study*”

Complete this checklist if the subject population will include adults with cognitive impairments.

This checklist does not need to be completed if the research doesn’t involve interactions or interventions with subjects and will be conducted under a waiver of consent.

1. Describe why the objectives of the study cannot be met without inclusion of adults with cognitive impairments.
2. Describe how capacity to consent will be evaluated.
3. If subjects may regain capacity to consent, or if subjects may have fluctuating capacity to consent, describe your plans to evaluate capacity to consent throughout the research and to obtain consent to continue participation if capacity is regained.
4. Describe your plans, if any, to provide information about the research to subjects and the steps you will take to assess understanding.
5. Describe your plans to obtain assent, including whether assent will be obtained from none, some, or all subjects.
6. Describe why risks to subjects are reasonable in relation to anticipated benefits to the subjects.
7. If this study involves a health or behavioral intervention, describe why the relation of the anticipated benefit to the risk of the research is at least as favorable to the subjects as that presented by alternative procedures.
8. Describe your plans for monitoring the well-being of subjects including any plans to withdraw subjects from the research if they appear to be unduly distressed.

PROTOCOL TITLE: “*Evaluating the efficacy of micro-fragmented adipose tissue and intra-articular corticosteroid injections for symptomatic knee osteoarthritis: a randomized, placebo controlled study*”

B. Children

Complete this checklist if the subject population will include children.

1. Select the category of research that you believe this research falls within and provide justification for any associated criteria. If there are different assessments for different groups of children or arms (e.g., placebo vs. drug), include a memo to provide an assessment for each group.

Research not involving greater than minimal risk. (*Minimal risk means that the probability and magnitude of harm or discomfort anticipated in the research are not greater in and of themselves than those ordinarily encountered in daily life or during the performance of routine physical or psychological examinations or tests.*)

Research involving greater than minimal risk but presenting the prospect of direct benefit to the individual subjects.

Provide justification for each of the following criteria:

- (1) The risk is justified by the anticipated benefit to the subjects:

- (2) The relation of the anticipated benefit to the risk is at least as favorable to the subjects as that presented by available alternative approaches:

Research involving greater than minimal risk and no prospect of direct benefit to individual subjects, but likely to yield generalizable knowledge about the subject's disorder or condition.

Provide justification for each of the following criteria:

- (1) The risk represents a minor increase over minimal risk:

- (2) The intervention or procedure presents experiences to subjects that are reasonably commensurate with those inherent in their actual or expected medical, dental, psychological, social, or educational situations:

- (3) The intervention or procedure is likely to yield generalizable knowledge about the subjects' disorder or condition which is of

PROTOCOL TITLE: “*Evaluating the efficacy of micro-fragmented adipose tissue and intra-articular corticosteroid injections for symptomatic knee osteoarthritis: a randomized, placebo controlled study*”

vital importance for the understanding or amelioration of the subjects' disorder or condition

C. Pregnant Women and Fetuses

Complete this checklist if the subject population will include pregnant women and fetuses.

This checklist does not need to be completed if the research is both minimal risk and is not conducted, funded, or otherwise subject to regulation by DHHS, DOD, EPA, or VA.

Provide justification for each of the following:

1. Where scientifically appropriate, preclinical studies, including studies on pregnant animals, and clinical studies, including studies on non-pregnant women, have been conducted and provide data for assessing potential risks to pregnant women and fetuses.
2. The risk to the fetus is caused solely by interventions or procedures that hold out the prospect of direct benefit for the woman or the fetus; *or*, if there is no such prospect of benefit, the risk to the fetus is not greater than minimal and the purpose of the research is the development of important biomedical knowledge which cannot be obtained by any other means.
3. Any risk is the least possible for achieving the objectives of the research.

D. Neonates of Uncertain Viability or Nonviable Neonates

Complete this checklist if the subject population will include neonates of uncertain viability.

Provide justification for each of the following:

1. Where scientifically appropriate, preclinical and clinical studies have been conducted and provide data for assessing potential risks to neonates.
2. Each individual providing consent is fully informed regarding the reasonably foreseeable impact of the research on the neonate.

PROTOCOL TITLE: “*Evaluating the efficacy of micro-fragmented adipose tissue and intra-articular corticosteroid injections for symptomatic knee osteoarthritis: a randomized, placebo controlled study*”

3. Individuals engaged in the research will have no part in determining the viability of a neonate.
4. The research holds out the prospect of enhancing the probability of survival of the neonate to the point of viability, and any risk is the least possible for achieving that objective, ***or***, the purpose of the research is the development of important biomedical knowledge which cannot be obtained by other means and there will be no added risk to the neonate resulting from the research

E. Nonviable Neonates

Complete this checklist if the subject population will include nonviable neonates.

Provide justification for each of the following:

1. Where scientifically appropriate, preclinical and clinical studies have been conducted and provide data for assessing potential risks to neonates.
2. Each individual providing consent is fully informed regarding the reasonably foreseeable impact of the research on the neonate.
3. Individuals engaged in the research will have no part in determining the viability of a neonate.
4. The purpose of the research is the development of important biomedical knowledge that cannot be obtained by other means.

Verify each of the following:

5. Vital functions of the neonate will not be artificially maintained
 True
 False
6. The research will not terminate the heartbeat or respiration of the neonate
 True
 False

PROTOCOL TITLE: “*Evaluating the efficacy of micro-fragmented adipose tissue and intra-articular corticosteroid injections for symptomatic knee osteoarthritis: a randomized, placebo controlled study*”

7. There will be no added risk to the neonate resulting from the research

True

False

F. Biomedical and Behavioral Research Involving Prisoners

Complete this checklist if the subject population will include prisoners.

Note: Minimal risk for research involving prisoners is the probability and magnitude of physical or psychological harm that is normally encountered in the daily lives, or in the routine medical, dental, or psychological examination of healthy persons.

1. Select and justify which allowable category of research involving prisoners this research falls within:

Study of the possible causes, effects, and processes of incarceration, and of criminal behavior, provided that the study presents no more than minimal risk and no more than inconvenience to the subjects

Study of prisons as institutional structures or of prisoners as incarcerated persons, provided that the study presents no more than minimal risk and no more than inconvenience to the subjects

Research on conditions particularly affecting prisoners as a class (for example, vaccine trials and other research on hepatitis which is much more prevalent in prisons than elsewhere; and research on social and psychological problems such as alcoholism, drug addiction, and sexual assaults)

Research on practices, both innovative and accepted, which have the intent and reasonable probability of improving the health or well-being of the subject

Epidemiologic studies in which the sole purpose is to describe the prevalence or incidence of a disease by identifying all cases or to study potential risk factor associations for a disease, the research presents no more than Minimal Risk and no more than inconvenience to the subjects, and Prisoners are not a particular focus of the research.

PROTOCOL TITLE: “*Evaluating the efficacy of micro-fragmented adipose tissue and intra-articular corticosteroid injections for symptomatic knee osteoarthritis: a randomized, placebo controlled study*”

2. Provide justification for each of the following regulatory criteria:

- a) Any possible advantages accruing to the prisoner through his or her participation in the research, when compared to the general living conditions, medical care, quality of food, amenities and opportunity for earnings in the prison, are not of such a magnitude that his or her ability to weigh the risks of the research against the value of such advantages in the limited choice environment of the prison is impaired
- b) The risks involved in the research are commensurate with risks that would be accepted by nonprisoner volunteers
- c) Procedures for the selection of subjects within the prison are fair to all prisoners and immune from arbitrary intervention by prison authorities or prisoners. Unless justification is provided, control subjects must be selected randomly from the group of available prisoners who meet the characteristics needed for that particular research project
- d) The information is presented in language which is understandable to the subject population
- e) Adequate assurance exists that parole boards will not take into account a prisoner's participation in the research in making decisions regarding parole, and each prisoner is clearly informed in advance that participation in the research will have no effect on his or her parole
- f) When appropriate, adequate provision has been made for follow up examination or care after research participation, taking into account the varying lengths of individual prisoners' sentences, and for informing participants of this fact

III. Medical Devices

Complete this checklist if the research evaluates the safety or effectiveness of a medical device. If more than one medical device is being evaluated, provide the requested information for each.

PROTOCOL TITLE: “*Evaluating the efficacy of micro-fragmented adipose tissue and intra-articular corticosteroid injections for symptomatic knee osteoarthritis: a randomized, placebo controlled study*”

A. Device Name: *Lipogems System*

B. Manufacturer: *Lipogems International S.p.A.*

C. Does the research involve a Significant Risk Device under an IDE?

Yes.

No

D. Is the research IDE-exempt?

Yes.

Lipogems® is marketed as an autologous adipose tissue transfer system. It has been cleared by the FDA twice, most recently on November 4th, 2016. In the most recent clearance, Lipogems® has been approved for harvest, concentration, and transfer of autologous adipose tissue for use in orthopaedic and arthroscopic procedures. Thus, it is considered on-label for those applications. The term “stem-cell” is not used as the device does not separate cells and tissue and all original components of the adipose tissue are present in the final concentrate after processing. In the clearance, it is stated that the cells and tissue microarchitecture are preserved, constituting a minimally manipulated product. With the existing FDA clearance, injection into the knee for arthritis or pain relief is considered within the scope of Lipogems®.

No

E. Does the research involve a Non-Significant Risk (NSR) Device?

Yes.

Lipogems® is marketed as an autologous adipose tissue transfer system. It has been cleared by the FDA twice, most recently on November 4th, 2016. In the most recent clearance, Lipogems® has been approved for harvest, concentration, and transfer of autologous adipose tissue for use in orthopaedic and arthroscopic procedures. Thus, it is considered on-label for those applications. The term “stem-cell” is not used as the device does not separate cells and tissue and all original components of the adipose tissue are present in the final concentrate after processing. In the clearance, it is stated that the cells and tissue microarchitecture are preserved, constituting a minimally manipulated product. With the existing FDA clearance, injection into the knee for arthritis or pain relief is considered within the scope of Lipogems®.

No

* This FDA guidance includes a description for when a device study is exempt from the IDE requirements:

<http://www.fda.gov/downloads/RegulatoryInformation/Guidances/UCM127067.pdf>

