- Individuals who agree to participate in this study will be enrolled during an initial screening visit which they will have independently sought and scheduled. Their participation will involve one procedure visit, two brief follow-up visits, and three online completion of surveys. We anticipate that it will take approximately 15 months from date of enrollment to complete each individual subject’s procedure and follow-up visits, allowing time for flexibility in scheduling based on the clinician and subject’s schedules.
- We estimate that it should take approximately three months to enroll 75 subjects. We anticipate this being feasible based on the four participating clinicians’ current schedules. Roughly, an orthopaedic surgeon may see upwards of 50 patients a day. Approximately 10% of these patients have knee OA and potentially qualify for the study.

PROTOCOL TITLE: “Evaluating the efficacy of micro-fragmented adipose tissue and intra-articular corticosteroid injections for symptomatic knee osteoarthritis: a randomized, placebo controlled study”

- *We anticipate the data analysis to take a maximum of two months following the completion of all data collection.*

7. Study Endpoints

- 7.1. *This study will conclude once all active, enrolled participants have completed their one-year follow-up.*
- 7.2. *Participants will be followed via standard of care and monitored at follow-up appointments. After we have had 10 participants enrolled in each group, we will do a preliminary evaluation of the available data.*
- 7.3. *Not applicable. We will not have exploratory endings.*

8. Research Setting

- 8.1. *Research will be conducted at the University of New Mexico Hospital Orthopaedic Clinics of [name], [name], [name] and [name], PA-C. Research, including all patient visits and procedures, will also be conducted at the CTSC.*
- 8.2. *Participants will be recruited from the patient population at the clinics of [name], [name], [name] and [name], PA-C at the University of New Mexico’s Orthopaedic Department. Since all potential participants will be independently seeking care for osteoarthritis, the participating clinicians and research staff will screen the patients for inclusion criteria during their standard examination.*
- 8.3. *Procedures and follow-up visits will be performed at the CTSC facilities on North Campus.*
- 8.4. *Not applicable. There will be no community advisory board*

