1. Participants will be screened prior to enrollment. Depending on their medical history and prior consultations, they will likely have a physical exam and x-rays of the affected knee(s). This is standard of care and will happen prior to enrollment in the study. X-ray images and medical data from these visits may be used for the purposes of analyzing statistical data.

PROTOCOL TITLE: "Evaluating the efficacy of micro-fragmented adipose tissue and intra-articular corticosteroid injections for symptomatic knee osteoarthritis: a randomized, placebo controlled study"

2. Upon enrollment, participants will be randomized to a treatment group and scheduled for their injection procedure.
3. At their injection visit, participants will complete the Western Ontario and McMaster Universities Osteoarthritis Index, a Visual Analog pain scale, and the Knee Injury and Osteoarthritis Outcome Score scales to establish a baseline. They will also fill out a medication log to document any medications that they take, including oral pain medications, although we will not be intervening with oral medications. They will complete these surveys and the log again at 2 weeks, 6 weeks, 3 months, 6 months, and 1 year after the injections

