- 25.1.24. *Not applicable. No permissions from individuals other than the patient will be required as all study participants are required to be eighteen years of age or older and capable of providing legally effective consent.*
- 25.1.25. *Not applicable. Children will not be enrolled in this study.*
- 25.1.26. *Not applicable. Children will not be enrolled in this study.*
- 25.1.27. *Not applicable. Children will not be enrolled in this study.*

26. Documentation of Consent

- 26.1. *This study will utilize an informed consent document in order to maintain documentation that the patient has given consent to participate in the study.*
- 26.2. *Not applicable. This study will not require the use of stored tissue samples.*
- 26.3. *Consent for this study will be obtained verbally and in-person by the participating clinicians, medical students, or research staff.*

PROTOCOL TITLE: “Evaluating the efficacy of micro-fragmented adipose tissue and intra-articular corticosteroid injections for symptomatic knee osteoarthritis: a randomized, placebo controlled study”

27. Study Test Results/Incidental Findings

- 27.1. **Individual Results:** Participants will be made aware of any physical findings in-person at their follow-up visits. Participants will still be kept blinded to their treatment group, as this is a single-blinded study. Once they have completed their one year follow-up questionnaire, the participants will be unblinded and those in the placebo group will be offered the opportunity to cross-over and receive a corticosteroid injection.
- 27.2. **Incidental Findings:** We do not anticipate coming across any incidental findings. If found, they will be disclosed to the patient.

28. Sharing Study Progress or Results with Subjects

- 28.1. Not applicable. Subjects will not be provided with trial progress while the study remains underway.
- 28.2. Participants will be made aware of what arm of the study they were assigned to. Lipogems® participants will have known since assigned to that group, as the procedure cannot be blinded. However, as this is a single-blinded study, placebo and corticosteroid participants will be made aware of their treatment at the conclusion of the study. Placebo participants will be given the option to receive a corticosteroid injection after they complete their 1 year questionnaire.

29. Inclusion of Vulnerable Populations

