- 29.1. Not applicable. The study does not involve individuals who are vulnerable to coercion or undue influence.

30. Community-Based Participatory Research

- 30.1. Not applicable. There will not be any community involvement in this study.

31. Research Involving American Indian/Native Populations

- 31.1. This is neither an inclusion or exclusion criteria for the study. Participants will be offered the chance to participate and the study will be explained at length to potential participants. Participants are free to decline the study if would prefer not to participate. They will continue to receive the standard of care.

32. Transnational Research

- 32.1. Not applicable. Our study will not involve transnational research.

33. Drugs or Devices

- 33.1. All drugs and devices are approved and cleared by the FDA.

Lipogems® (brand name: Lipogems System, manufacturer: Lipogems International S.p.A., no generic currently on the market) device kits will be sent to [name] at the University of New Mexico Hospital after a participant has enrolled in the study and been randomly assigned to receive

PROTOCOL TITLE: “*Evaluating the efficacy of micro-fragmented adipose tissue and intra-articular corticosteroid injections for symptomatic knee osteoarthritis: a randomized, placebo controlled study*”

Lipogems®. Treatment drugs and devices will be stored, handled, and dispensed by a licensed pharmacist at UNM IDS Pharmacy. Drugs will be stored under proper conditions of sanitation, temperature, light, moisture, ventilation, segregation, safety, and security. These items will be stored in accordance with existing hospital policy and storage requirements. [name], [name], and [name] will be authorized to perform Lipogems procedures. [name], [name], [name] and [name], PA-C are authorized to give corticosteroid or placebo injections.

33.2. *Not applicable. No drugs or devices in this study are investigational. They are all marketed and none are being used off-label.*

33.3. *Not applicable.*

PROTOCOL TITLE: “*Evaluating the efficacy of micro-fragmented adipose tissue and intra-articular corticosteroid injections for symptomatic knee osteoarthritis: a randomized, placebo controlled study*”

Checklist Section

This section contains checklists to provide information on a variety of topics that require special determinations by the IRB. Please complete all checklists relevant to your research.

I. Waivers or Alterations of Consent, Assent, and HIPAA Authorization

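### Randomised participants who are never injected have no follow-up schedule and drop out of the analysis, and this loss can differ by arm because the Lipogems allocation is known before the injection

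*Combined protocol and SAP*

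**What the plan says.** The order of events has to be pieced together from several sections.

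- **Enrolment (6.1):** individuals "will be enrolled during an initial screening visit".
- **Randomisation (12.1 item 2):** "Upon enrollment, participants will be randomized to a treatment group and scheduled for their injection procedure".
- **Kit supply (33.1):** Lipogems kits are sent "after a participant has enrolled in the study and been randomly assigned to receive" that treatment, so a wait is built into that arm.
- **Knowledge of allocation (28.2):** Lipogems "participants will have known since assigned to that group, as the procedure cannot be blinded". Corticosteroid and saline participants are blinded (3.2).
- **Outcome assessment (12.1 items 3 and 5):** WOMAC, VAS and KOOS are first completed at the injection visit. For the later rounds: "They will complete these surveys and the log again at 2 weeks, 6 weeks, 3 months, 6 months, and 1 year after the injections".
- **Duration (6.1):** "approximately 15 months from date of enrollment to complete" procedure and follow-up, "allowing time for flexibility in scheduling". No maximum interval from randomisation to injection is stated.
- **Withdrawal (15.1, 15.3, 15.4):** people who will not book, or who do not answer booking requests, are withdrawn. Data already collected are normally kept. Partial withdrawal with online questionnaires is allowed for someone who no longer wants follow-up visits.
- **Analysis (13.1):** mixed-effects models compare post-treatment trajectories between pairs of groups. No analysis set is named.

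Section 25.1.15 is out of line with this sequence. It places consent at the procedure visit and counts four follow-up examinations, where 12.1 has two in-person visits.

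**The concern.** Between randomisation and injection, one arm knows that it faces an abdominal fat harvest and the other two do not. People can change their minds in that gap, and what they would be refusing differs by arm. The protocol collects nothing from them in the gap, gives them no assessment dates afterwards, and tells staff to withdraw those who will not schedule.

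The comparison that results is between people who accepted their assigned procedure, not between the groups formed by randomisation. If willingness to go ahead is related to pain or motivation, the Lipogems contrasts are biased. The mixed model cannot correct this, because it has no post-randomisation score for these people to work with.

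**Working it through.** **Step 1. Length of the gap.** Inputs are 15 months from enrolment (6.1, repeated in 9.3) and 1 year of follow-up from injection (12.1). 15 - 12 = 3 months. This is a ceiling implied by two planning figures, not an interval the plan states.

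**Step 2. What each kind of non-injected participant contributes.**

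| Participant | Scores held | Follow-up dates defined? | Information on post-treatment difference |
|---|---|---|---|
| Leaves before the injection visit | None (only the intake pain score used for eligibility) | No | None |
| Completes the questionnaires at the injection visit, then declines | Baseline | No | None from follow-up |
| Injected, then lost | Baseline and any later scores | Yes | Partial; usable by the mixed model |

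Only the third row is the kind of drop-out that a longitudinal model can absorb. The compensation for drop-outs expected in 5.3 is in any case a claim about power, not about selection.

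**Step 3. Possible bias.** Let a fraction p of an arm be lost, with mean outcome S + D, where S is the mean of those who stay. The mean of the full randomised arm is (1 - p)S + p(S + D) = S + pD. Analysing only those who stay is therefore off by p × D. The documents give neither p nor D, so the values below are assumptions.

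| p | D = 5 | D = 10 | D = 15 | D = 20 |
|---|---|---|---|---|
| 10% | 0.5 | 1.0 | 1.5 | 2.0 |
| 20% | 1.0 | 2.0 | 3.0 | 4.0 |

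These are VAS points on the 100-point scale, against the 15-point difference used for planning. The direction depends on who leaves.

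**Step 4. Power.** The plan's own n is reproduced first. With a difference of 15, SD 20, 80% power and one-sided 5%, n = 2 × (1.645 + 0.842)² × 20² / 15² ≈ 22 per group, the figure in 13.2. The two-sided equivalent is 28. Now take 25 in the comparator arm and 25 minus the losses in the Lipogems arm. Power is Φ(15 / [20√(1/25 + 1/n)] - z), where n is the number left in the Lipogems arm:

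| Lost before injection | n | One-sided | Two-sided |
|---|---|---|---|
| 0 | 25 | 84% | 76% |
| 2 (8%) | 23 | 83% | 74% |
| 5 (20%) | 20 | 80% | 71% |
| 7 (28%) | 18 | 78% | 68% |

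The loss of power is modest. Selection is the main issue.

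**The case against.** Several points on the other side are fair.

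- **The gap may be short.** A reader might infer that participants wait three months. The documents do not say so: the slack in 6.1 covers all scheduling, including a late 1-year assessment. Section 25.1.15, read alone, would leave no gap, but it conflicts with 6.1, 12.1, 25.1.4 and 33.1. This limits how many people might be lost. It does not change what happens to those who are.
- **Sample size.** A reader might infer that four losses from 25 leave 21 and breach the minimum of 22. That assumes exactly 25 are randomised. Sections 5.2 and 9.3 count 75 completers, 5.3 aims for 25 or more per arm, and 16.7 provides codes up to 100, although 6.1 speaks of enrolling 75. A breach is not shown. Extra enrolment would restore numbers but would not remove selection.
- **No exclusion is written.** A reader might infer that the plan deliberately analyses only treated participants. It does not state that. The exclusion follows from having no scores, no dates and no analysis set. The 15.1 rule may have been meant for follow-up visits only, but its wording does not limit it to them.
- **Existing safeguards.** Consent with teach-back before enrolment (section 25) should screen out some people unwilling to have the harvest. Partial withdrawal in 15.3 already allows questionnaires without visits, but sets no time origin for someone never injected.
- **Scope.** The corticosteroid-saline comparison is largely untouched, because those two arms are blinded to each other.

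**Conclusion.** The point stands in this form: as written, the plan can lose randomised participants before treatment, in numbers that may depend on arm, and it has no means of recovering their outcomes. It bears mainly on Lipogems versus placebo and Lipogems versus corticosteroid. The sequence, the known Lipogems allocation, the injection-based timing and the withdrawal rule are all explicit. That these participants fall out of the analysis is a consequence of those provisions.

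The size cannot be determined from the documents. The 0.5-4 point range rests entirely on assumed loss and outcome differences; it is small to moderate beside the 15-point target. This should be corrected before enrolment, because the missing scores cannot be collected afterwards.

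**What to change.** 1. **12.1 items 3 and 5:** send randomised but uninjected participants the same questionnaires, online or by phone, at the same five times. Count from the scheduled injection date or, if none was booked, from a fixed date after randomisation set the same way in all arms. Stop only if consent to data collection is withdrawn.
2. **15.1 and 15.3:** state that declining or not scheduling the injection does not by itself end questionnaire data collection. Otherwise staff would be told both to withdraw and to follow the same person.
3. **13.1:** make the primary analysis all randomised participants by assigned arm, and report the number not injected by arm with reasons.
4. **25.1.15:** reconcile the place of consent and the number of follow-up examinations with 6.1, 12.1 and 25.1.4.

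**Cost.** Protocol wording and a RedCap schedule that can run without an injection date; no new visits, since online and phone completion are already planned.

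The statistical cost is dilution. If 4 of 25 in an arm are untreated and have no effect, a 15-point contrast becomes 15 × 21/25 = 12.6, a reduction of 2.4 points, which lies within the range of the bias being addressed. The as-randomised comparison is still the one that randomisation protects. An as-treated analysis can be kept as a sensitivity analysis.
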